3. OBJECTIVES AND ENDPOINTS

The objectives which will be evaluated in this study and endpoints associated with each objective are provided in Table 2.

Table 2: Study Objectives and Endpoints

Table 2: Study Objectives and Endpoints		
Objectives	Endpoints	
Primary		
To evaluate the safety and reactogenicity of mRNA-1020, mRNA-1030, and mRNA-1010	Frequency and grade of each solicited local and systemic reactogenicity AR during a 7-day follow-up period post-vaccination	
	• Frequency and severity of any unsolicited AEs during the 28-day follow-up period post-vaccination	
	 Frequency of any SAEs, AESIs, MAAEs, and AEs leading to withdrawal from Day 1 through Day 181/EoS 	
	Safety laboratory abnormalities through 7 days post- vaccination	
To evaluate the humoral immunogenicity of mRNA-1020, mRNA-1030, and mRNA-1010 against vaccine-matched influenza A and B strains at Day 29	 GMT and GMFR, comparing Day 29 to Day 1 (baseline), and percentage of participants with seroconversion, defined as a Day 29 titer ≥ 1:40 if baseline is < 1:10 or a 4-fold or greater rise if baseline is ≥ 1:10 in anti-HA antibodies measured by HAI assay GMT and GMFR of anti-NA measured by NAI assay 	
	at Day 1 and Day 29 and percentage of participants with a change in the Day 29 titer of at least 2-/3-/4-fold rise, defined as ≥ 2 -/3-/4-fold of the LLOQ if the Day 1 titer is $<$ LLOQ; or ≥ 2 -/3-/4-fold of the Day 1 titer if the Day 1 titer is \geq LLOQ	
Secondary		
To evaluate the humoral immunogenicity of mRNA-1020, mRNA-1030, and mRNA-1010 against vaccine-matched influenza A and B strains at all evaluable humoral immunogenicity time points	GMT and GMFR (compared to Day 1) of anti-HA or anti-NA antibodies as measured by HAI, NAI, and/or MN assays	
Exploratory (may be performed)		
To evaluate the humoral immunogenicity against vaccine-mismatched influenza A and B strains	GMT and GMFR (compared to Day 1) of anti-HA or anti-NA antibodies as measured by HAI, NAI, or MN assays against vaccine-mismatched strains	

Objectives	Endpoints
To evaluate cellular immunogenicity in a subset of participants	Frequency, magnitude, and phenotype of virus- specific T-cell and B-cell responses measured by flow cytometry or other methods, and to perform targeted repertoire analysis of T-cells and B-cells after vaccination
To further characterize antibody responses, for example, Fc-mediated function, avidity, or epitope specificity	Frequency, specificities, or other endpoints to be determined, for the further characterization of antibody responses
To assess the occurrence of clinical influenza in study participants and characterize their immune response to infection and viral isolates	Frequency of clinical influenza and immune responses
Sample collection to perform passive transfer studies in preclinical animal models	Transfer of human sera into mice with subsequent influenza virus challenge to observe protection from morbidity and mortality conferred by NA-specific antibodies

Abbreviations: AE = adverse event; AESI = adverse event of special interest; AR = adverse reaction; EoS = end of study; Fc = fragment crystallizable; GMFR = geometric mean fold rise; GMT = geometric mean titer; HA = hemagglutinin; HAI = hemagglutination inhibition; LLOQ = lower limit of quantification; MAAE = medically attended adverse event; MN = microneutralization; NA = neuraminidase; NAI = neuraminidase inhibition; SAE = serious adverse event.

4. STUDY DESIGN

4.1. General Design

The study will be a Phase 1/2, randomized, observer-blind, dose-ranging study to evaluate the safety, reactogenicity, and immunogenicity of mRNA-1020 (CCI) and mRNA-1030 (CCI) in healthy adults 18 to 75 years of age. Enrollment in study arms will proceed in parallel with randomization (Figure 1) of all dose levels of mRNA-1020 and mRNA-1030 (Study Arms 1 to 6), the mRNA-1010 Comparator Arm (Study Arm 7), and the Flublok Comparator Arm (Study Arm 8). The study will randomize approximately 70 healthy adult participants into each study arm with a balanced age group representation stratified approximately 1:1 into age groups of 18 to < 50 years of age and \ge 50 to \le 75 years of age.

The vaccines to be tested contain mRNAs encoding for the surface glycoproteins of the strains recommended by the WHO for 2021/22 NH cell- or recombinant-based vaccines:

- A/Wisconsin/588/2019(H1N1)pdm09
- A/Cambodia/e0826360/2020(H3N2)
- B/Washington/02/2019 (B/Victoria lineage)
- B/Phuket/3073/2013 (B/Yamagata lineage)

Study visits will consist of a Screening Visit (up to 28 days before the Day 1 visit), Vaccination Visit at Day 1, and subsequent study visits on Day 4, Day 8, Day 29 (Month 1), and Day 181/end of study (EoS; Month 6), with up to 7 months of study participation (Table 1). Unscheduled visits for potential ILI symptoms will include testing with a multiplex respiratory infection panel (Biofire or similar).

Immunizations for the study are planned during the NH spring, when influenza infection rates are typically low or declining. Approximately 560 participants will be randomized to receive a single dose of either one of the 2 next-generation candidate vaccines (mRNA-1020 or mRNA-1030) at different dose levels, a single dose of the first-generation candidate vaccine (mRNA-1010), or Flublok, a licensed enhanced seasonal influenza vaccine comparator (8 study arms total). Three different dose levels (CCI (mRNA-1020), 3 different dose levels (CCI (mRNA-1030), and a single dose level of mRNA-1010 (50 µg total mRNA) will be assessed. A description of the mass ratios for the dose levels are provided in Table 3. The target number of participants in each arm and the randomization ratio can be found in Table 4.

ModernaTX, Inc. 16 Feb 2022 mRNA-1020 and mRNA-1030

Protocol: mRNA-1020-P101 Amendment 1

Table 3:	Mass	Ratios	for	Dose	Lev	els
----------	------	--------	-----	------	-----	-----

Program	Valency	Description of Encoded Antigens	Mass Ratio ^a
mRNA-1010	4	Four HA antigens	CCI
mRNA-1020	8	Four HA antigens Four NA antigens	CCI
mRNA-1030	8	Four HA antigens Four NA antigens	CCI

Individual mass ratios are rounded for reporting, and the total of reported values may not equal 100%.

Table 4: Study Arms and Dose Levels

Vaccination Group	Group Name	Antigen(s)	Total Dose	N (total)	Age 18-49	Age 50- 75
1	mRNA-1030	HA+NA	CCI	70	35	35
2	mRNA-1020	HA+NA	CCI	70	35	35
3	mRNA-1030	HA+NA	CCI	70	35	35
4	mRNA-1020	HA+NA	CCI	70	35	35
5	mRNA-1030	HA+NA	CCI	70	35	35
6	mRNA-1020	HA+NA	CCI	70	35	35
7	mRNA-1010 (HA only comparator)	HA only	50 μg	70	35	35
8	Flublok (active comparator)	HA only	180 μg	70	35	35
Total				560	280	280

Abbreviations: HA = hemagglutinin; mRNA = messenger RNA; NA = neuraminidase.

4.2. Scientific Rationale for Study Design

This study is designed as an observer-blind study. Participants in Vaccination Groups 1, 3, and 5 will receive mRNA-1030 vaccine and participants in Groups 2, 4, and 6 will receive mRNA-1020 vaccine. mRNA-1010 and Flublok will be used as comparators for descriptive comparisons of safety and immunogenicity.

All participants will provide nasopharyngeal (NP) swab samples before the injection on Day 1 for assessment of asymptomatic infection with respiratory pathogens, including influenza virus and SARS-CoV-2, as influenza or COVID-19 symptoms may confound reactogenicity assessments (CDC 2021a). Furthermore, if a participant experiences any signs or symptoms suggesting ILI and/or COVID-19, an additional NP swab sample will be collected to confirm the diagnosis via reverse transcription polymerase chain reaction (RT-PCR). Clinical information may be collected to evaluate the severity of the clinical case (CDC 2020b).

4.3. Choice of Vaccine Dose

No clinical studies of mRNA-1020 or mRNA-1030 have been conducted to date.

Previous studies of the Sponsor's mRNA/LNP SM-102 platform have assessed dose levels as high as 250 μg for mRNA-1273, a SARS-CoV-2 vaccine (Jackson et al 2020, NCT04283461), and mRNA-1893, a Zika vaccine (unpublished data, NCT04917861). Additionally, doses up to 300 μg of the multivalent mRNA-1647, a cytomegalovirus vaccine (unpublished data, NCT03382405), and the multivalent mRNA-1653, a combination vaccine against human metapneumovirus and parainfluenza virus type 3 (unpublished data, NCT03392389), have been tested in Phase 1 studies. The vaccines were generally well tolerated at these dose levels.

The Sponsor has previously evaluated the immunogenicity of 2 mRNA vaccines containing the HA glycoprotein from the H10N8 and H7N9 influenza viruses. Although differences in the mRNA/LNP platform and the administration schedule (2 doses were given 3 weeks apart) limit extrapolation of the safety data, these mRNA vaccines against H10N8 and H7N9 influenza viruses elicited robust humoral immune responses and were well tolerated up to dose levels of 100 µg (for each HA type; Feldman et al 2019).

The Sponsor's Phase 1/2 mRNA-1010 P101 study (NCT04956575) is currently ongoing. No significant safety concerns have been observed in the ongoing Phase 1/2 portion of mRNA-1010-P101 study upon review of safety data up to 29 days by the DSMB. In that study, 45 participants in each group received 50 μg, 100 μg, or 200 μg doses of mRNA-1010. The local and systemic reactogenicity were mostly mild to moderate in severity. There were no Grade 4 adverse reactions or SAEs assessed by the Investigator as related to the study vaccine. The 3 doses of mRNA-1010 elicited comparable humoral immunogenicity responses. In addition, the Phase 2 NH portion of mRNA-1010-P101 study has enrolled 498 adults in a Phase 2 NH cohort in 4 groups: 25 μg mRNA-1010 (n=151), 50 μg mRNA-1010 (n=147), 100 μg mRNA-1010 (n=147), and Afluria (n=53). The interim analysis of safety data through Day 29 demonstrated no significant safety concerns. The frequency and severity of the reports of solicited adverse reactions (ARs) in the mRNA-1010 groups were acceptable across all dose levels. Based on this data, the highest dose level for mRNA-1020 and mRNA-1030 (Col

This first-in-human clinical study of mRNA-1020 or mRNA-1030 vaccines will evaluate the immunogenicity of mRNA-1020 and mRNA-1030 at proposed total dose levels of 50, 100, 150 and 25, 50, 100 μ g total mRNA, respectively, administered as a single IM injection in generally healthy adults \geq 18 to \leq 75 years of age.

ModernaTX, Inc. 16 Feb 2022
Protocol: mRNA-1020-P101 Amendment 1 mRNA-1020 and mRNA-1030

4.4. End of Study Definition

A participant is considered to have completed the study if he or she has completed all phases of the study including last scheduled procedure(s) as shown in the schedule of events (SoE), Table 1.

The EoS is defined as completion of the last visit of the last participant in the study or last scheduled procedure(s) as shown in the SoE (Table 1) for the last participant in the study.

5. STUDY POPULATION

Prospective approval of protocol deviations to recruitment and enrollment criteria, also known as protocol waivers or exemptions, is not permitted.

5.1. Inclusion Criteria

Each participant must meet all of the following criteria to be enrolled in this study:

- 1. Adults 18 to 75 years of age at the time of consent (Screening Visit). Participants may be rescreened if they are not medically stable at the Screening Visit.
- 2. Investigator assessment that participant understands and is willing and physically able to comply with protocol-mandated follow-up, including all procedures.
- 3. Participant has provided written informed consent for participation in this study, including all evaluations and procedures as specified in this protocol.
- 4. Body mass index of 18 kg/m² to 35 kg/m² (inclusive) at the Screening Visit.
- 5. Female participants of nonchildbearing potential may be enrolled in the study. Nonchildbearing potential is defined as post-menopausal or permanently sterilized (Appendix 2 [Section 11.2]). A follicle-stimulating hormone (FSH) level should be measured at the discretion of the Investigator, if necessary, to confirm postmenopausal status.
- 6. Female participants of childbearing potential may be enrolled in the study if the participant fulfills all the following criteria:
 - Has a negative pregnancy test at the Screening Visit and on the day of vaccination (Day 1).
 - Has practiced adequate contraception or has abstained from all activities that could result in pregnancy for at least 28 days prior to Day 1 (Appendix 2 [Section 11.2]).
 Adequate female contraception is defined as consistent and correct use of an FDA approved contraceptive method in accordance with the product label.
 - Has agreed to continue adequate contraception through 90 days following vaccine administration.
 - Is not currently breastfeeding.

5.2. Exclusion Criteria

Participants meeting any of the following criteria will be excluded from the study:

- 1. Participant has had close contact to someone with SARS-CoV-2 infection or COVID-19 as defined by the CDC or has had a positive SARS-CoV-2 test in the past 10 days prior to the Screening Visit (CDC 2020c, CDC 2021b).
- 2. Clinical screening laboratory values (total white blood cell [WBC] count, hemoglobin, platelets, alanine aminotransferase, aspartate aminotransferase, creatinine, alkaline phosphatase, and total bilirubin) > Grade 1 in laboratory abnormality.

3. Participant is acutely ill or febrile (temperature $\geq 38.0^{\circ}\text{C}/100.4^{\circ}\text{F}$) 72 hours prior to or at the Screening Visit or Day 1. Participants meeting this criterion may be rescheduled within the 28-day screening window and will retain their initially assigned participant number.

- 4. History of a diagnosis or condition that, in the judgment of the Investigator, is clinically unstable or may affect participant safety, assessment of safety endpoints, assessment of immune response, or adherence to study procedures. Clinically unstable is defined as a diagnosis or condition requiring significant changes in management or medication within the 60 days prior to screening and includes ongoing workup of an undiagnosed illness that could lead to a new diagnosis or condition.
- 5. History of myocarditis, pericarditis, or myopericarditis.
- 6. Reported history of congenital or acquired immunodeficiency, immunosuppressive condition, or immune-mediated disease.
- 7. Dermatologic conditions that could affect local solicited AR assessments (eg. tattoos, psoriasis patches affecting skin over the deltoid areas).
- 8. Reported history of anaphylaxis or severe hypersensitivity reaction after receipt of any components of mRNA- or cell-based influenza (eg, Flublok) vaccine.
- 9. Reported history of bleeding disorder that is considered a contraindication to IM injection or phlebotomy.
- 10. Any medical, psychiatric, or occupational condition, including reported history of substance abuse, that, in the opinion of the Investigator, might pose additional risk due to participation in the study or could interfere with the interpretation of study results. Asymptomatic conditions and conditions with no evidence of end organ involvement (eg, mild hypertension, dyslipidemia) are not exclusionary, provided that they are being appropriately managed and are clinically stable (ie, unlikely to result in symptomatic illness within the time course of this study). Illnesses or conditions may be exclusionary, even if otherwise stable, due to therapies used to treat them (eg, immune-modifying treatments), at the discretion of the Investigator.
- 11. Participant has received systemic immunosuppressants or immune-modifying drugs for > 14 days in total within 180 days prior to screening (for corticosteroids ≥ 10 mg/day of prednisone equivalent) or is anticipating the need for immunosuppressive treatment at any time during participation in the study.
- 12. Participant has received or plans to receive any licensed or authorized vaccine, including COVID-19 vaccines, ≤ 28 days prior to the study injection (Day 1) or plans to receive a licensed or authorized vaccine within 28 days after the study injection.
- 13. Participant has received a NH 2021-2022 seasonal influenza vaccine or any other influenza vaccine within 180 days prior to Day 1.
- 14. Participant tested positive for influenza by CDC-recommended testing methods within 180 days prior to Day 1 (CDC 2020d).

ModernaTX, Inc. 16 Feb 2022
Protocol: mRNA-1020-P101 Amendment 1 mRNA-1020 and mRNA-1030

15. Participant has received systemic immunoglobulins or blood products within 90 days prior to the Screening Visit or plans to receive during the study.

- 16. Diagnosis of malignancy within previous 10 years (excluding nonmelanoma skin cancer).
- 17. Participant has donated ≥ 450 mL of blood products within 28 days prior to the Screening Visit or plans to donate blood products during the study.
- 18. Participated in an interventional clinical study within 28 days prior to the Screening Visit based on the medical history interview or plans to do so while participating in this study.
- 19. Participant is an immediate family member or household member of study personnel, study site staff, or Sponsor personnel.

5.3. Lifestyle Restrictions

Participants must not eat or drink anything hot or cold within 10 minutes before oral temperature is taken. Participants in the study should defer vaccination with licensed or authorized vaccines, including COVID-19 vaccines, until after completion of their Day 29 Visit, if a licensed or authorized vaccine is available and they choose to receive it.

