1.3. Schedule of Events

Table 1: Schedule of Events

Visit Number		1	2	3	4	5, 6, 7, and 8	9	USV
Type of Visit	С	С	С	С	С	SC	С	С
Month Time Point					M1	M2-M5	M6	Up to M6
Visit Day	Screeninga	D1 ^a (Baseline)	D4	D8	D29	D57, D91, D121, D151	D181/EoS	N/A
Window Allowance (Days)	-28	-	-2	-2 or +1	-7 to +2	±5	±14	N/A
Informed consent form, demographics, medical history ^b	X							
Inclusion/exclusion criteria	X	X						
Blood collection for safety laboratory samples ^c	X			X				
Full physical examination ^d	X							
Symptom-directed physical examination ^{d,e}		X		X	X		X	X
Injection site and axillary lymph node assessment (injected arm)		X						
Vital sign measurements ^e	X	X						
ECG ^f		X						
Pregnancy testing ^g	X	X						
Randomization		X						
Study vaccination (including 60-minute postdose observation period)		X ^h						
Blood collection for humoral immunogenicity ⁱ		X		X	X		X	
Blood collection for cellular immunogenicity ⁱ		X		X	X			
Optional blood collection for genomics		X						
Optional blood collection for transcriptomics		X		X	X			
Blood sample for biomarker analysis ^j			X					
Nasopharyngeal swab for virus detection ^k		X						X
eDiary activation for recording solicited ARs (7 days) ^l		X						

Protocol: mRNA-1020-P101 Amendment 1 mRNA-1020 and mRNA-1030

Visit Number		1	2	3	4	5, 6, 7, and 8	9	USV
Type of Visit	С	С	С	С	С	SC	С	С
Month Time Point					M1	M2-M5	M6	Up to M6
Visit Day	Screeninga	D1 ^a (Baseline)	D4	D8	D29	D57, D91, D121, D151	D181/EoS	N/A
Window Allowance (Days)	-28	-	-2	-2 or +1	-7 to +2	±5	±14	N/A
Review of eDiary				X				
Follow-up safety call ^m						X		
Recording of all unsolicited AEs		X		X	X			
Recording of SAEs, AESIs, MAAEs, and AEs leading to study withdrawal		X		X	X	X	X	X
Recording of concomitant medications and nonstudy vaccinations ⁿ	X	X		X	X	X	X	X
Study completion							X	

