- Any concomitant medications relevant to or for the treatment of an SAE, adverse event of special interest (AESI; Section 8.4.6), a medically attended AE (MAAE; Section 8.4.4), or an AE leading to withdrawal from Day 1 through Day 181/EoS.
- The participant will be asked in the eDiary if they have taken any antipyretic or analgesic medication to treat or prevent fever or pain within 7 days after the study vaccination, including the day of injection. Reported antipyretic or analgesic medications should be recorded in the source document by the study site staff during the study visits after vaccination or via other participant interactions (eg, telephone calls).

If a participant takes a prohibited drug therapy, the Investigator and the contract research organization's (CRO's) medical monitor will make a joint decision about continuing or withholding the study vaccination of the participant based on the time the medication was administered, the drug's pharmacology and pharmacokinetics, and whether use of the medication will compromise the participant's safety or interpretation of the data. It is the Investigator's responsibility to ensure that details regarding the concomitant medications are adequately recorded in the eCRF.

All medication and interventions necessary for the appropriate care of the study participant should be administered and appropriately documented along with the AE for which the treatment was initiated.

6.5.3. Concomitant Medications and Vaccines that May Lead to the Elimination of a Participant from Per-Protocol Analyses

The use of the following concomitant medications and/or vaccines will not require withdrawal of the participant from the study but may determine a participant's evaluability in the Per-Protocol (PP) analysis (see Table 8 for definition of PP Set):

- Any investigational or nonregistered product (drug or vaccine) other than the study vaccine used during the study period.
- Immunosuppressants or other immune-modifying drugs administered chronically (ie, more than 14 days in total) during the study period. For corticosteroids, this will mean that ≥ 10 mg/day of prednisone or equivalent is not permitted. Inhaled, nasal, and topical steroids are allowed
- Long-acting immune-modifying drugs administered at any time during the study period (eg, infliximab).
- An authorized or licensed vaccine administered within 28 days after the study vaccination (Section 5.2).

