6.2.6 Analysis Periods for Safety Analyses

The following analysis periods for safety analyses will be used in this study:

- 7 days following vaccination: this period includes the day of vaccination and 6 subsequent days. This analysis period will be used for solicited local and systemic ARs that occur during this time.
- 28 days following vaccination: this period includes the day of vaccination and 27 subsequent days. This analysis period will be used for unsolicited AEs.
- Overall period: this analysis period starts on Day 1 and continues through the earliest of the following: Day 181/study completion, discontinuation from the study, or death.

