 - The medication end date is after the date of injection or is missing AND the start year of the medication coincide with the start year of the injection. In this case, use the date of injection
- If Day, Month, and Year are all missing, the date will not be imputed, but the medication will be treated as though it began prior to the injection for purposes of determining if status as prior or concomitant.

2. Missing or partial medication end date:

- If only Day is missing, use the earliest date of (last day of the month, study completion, discontinuation from the study, or death).
- If Day and Month are both missing, use the earliest date of (last day of the year, study completion, discontinuation from the study, or death).
- If Day, Month, and Year are all missing, the date will not be imputed, but the medication will be flagged as a continuing medication.

In summary, the prior, concomitant, or post categorization of a medication is described in [Table 5](#) below.

Table 5 Prior, Concomitant, and Post Categorization of Medications and Non-Study Vaccinations

Medication Start Date	Medication End Date		
	< Injection Date of IP	\geq Injection Date and \leq Injection Date + 27 Days	> Injection Date + 27 days [1]
< Injection date of IP [2]	P	P, C	P, C, A
\geq Injection date and \leq Injection date + 27 days	-	C	C, A
> Injection date + 27 days	-	-	A

A = Post; C = Concomitant; P = Prior

[1] includes medications with completely missing end date

[2] includes medications with completely missing start date

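### Vaccine deferral in Protocol 5.3 can end on Day 22, inside the 28 days used for per-protocol evaluability and for unsolicited AEs

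*Protocol*

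**What the plan says.** Protocol 5.3 ties the end of deferral to an event. Participants "should defer vaccination with licensed or authorized vaccines, including COVID-19 vaccines, until after completion of their Day 29 Visit", with no minimum number of days after injection. Table 1 gives the Day 29 Visit a window of −7 to +2 days.

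Three other places use a fixed 28-day period:

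- Exclusion criterion 12 (Protocol 5.2) bars anyone who "plans to receive a licensed or authorized vaccine within 28 days after the study injection".
- Protocol 6.5.3 lists "An authorized or licensed vaccine administered within 28 days after the study vaccination (Section 5.2") among exposures whose use "will not require withdrawal of the participant from the study but may determine" evaluability in the PP analysis.
- SAP 6.2.6 defines the unsolicited AE period: "28 days following vaccination: this period includes the day of vaccination and 27 subsequent days".

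The last day of the 28 is not the same everywhere. SAP 6.2.6 and Protocol 8.1 end it on injection day + 27, which is Day 28. SAP Appendix C, Table 5, titled "Prior, Concomitant, and Post Categorization of Medications and Non-Study Vaccinations", uses the same boundary ("> Injection Date + 27 days"). Protocol 8.4.14 collects unsolicited AEs through 28 days after the injection, which can be read as Day 29.

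**The concern.** Section 5.3 is the instruction on when participants may have another vaccine, and it can release them up to a week before the plan's own 28-day limits expire. Two things are at stake.

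- **PP evaluability.** The PP Set is the primary immunogenicity set and is defined once, not per time point. A participant who did as told could still meet the 6.5.3 trigger. Excluding that person would discard a valid Day 29 titer. With 35 planned per arm and age group, one loss is 1/35 = 2.9% of a cell.
- **Unsolicited AEs.** Their frequency over 28 days is a primary safety endpoint. SAP 6.2.6 does not end the period at a non-study vaccination, and the treatment-emergent definition in SAP 6.4.1 does not set aside events that follow one. A reaction to the other vaccine could be counted against the study vaccine.

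**Working it through.** **Inputs**

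- Injection date is Day 1, so days after injection = study day − 1 (SAP 6.2.4).
- Day 29 Visit window: −7 to +2 days (Protocol Table 1).
- PP window for the Day 29 sample: −7/+14 days, stated as 21 to 42 days after injection (SAP 5.3).
- Last day of the 28-day period, E: Day 28 (injection day + 27) or Day 29 (28 days after injection).

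**The plan's own figure.** 29 − 7 = Day 22, and 22 − 1 = 21 days after injection. 29 + 14 = Day 43, and 43 − 1 = 42 days after injection. This matches SAP 5.3 and shows that a Day 22 visit is compliant and acceptable for the PP Set.

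**Permitted visit days.** 29 − 7 = 22 and 29 + 2 = 31, so there are 31 − 22 + 1 = 10 days.

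**Overlap.** For a visit on Day v, suppose another vaccine is possible from Day v + k (k = 0, same day; k = 1, next day). The days on which 5.3 allows that vaccine while the 28-day period is still running are

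max(0, E − (v + k) + 1).

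| Visit day v | E = 28, k = 0 | E = 28, k = 1 | E = 29, k = 0 | E = 29, k = 1 |
|---|---|---|---|---|
| 22 | 7 | 6 | 8 | 7 |
| 23 | 6 | 5 | 7 | 6 |
| 24 | 5 | 4 | 6 | 5 |
| 25 | 4 | 3 | 5 | 4 |
| 26 | 3 | 2 | 4 | 3 |
| 27 | 2 | 1 | 3 | 2 |
| 28 | 1 | 0 | 2 | 1 |
| 29 | 0 | 0 | 1 | 0 |
| 30 | 0 | 0 | 0 | 0 |
| 31 | 0 | 0 | 0 | 0 |
| Visit days with overlap | 7 of 10 | 6 of 10 | 8 of 10 | 7 of 10 |

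For the unsolicited AE period, the SAP 6.2.6 definition (E = 28) gives 6 or 7 of 10. Reading Protocol 8.4.14 as Day 29 gives 7 or 8 of 10. On the Day 29 reading with same-day vaccination, even a visit exactly on Day 29 leaves one day of overlap.

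**With deferral to Day 30.** The first permitted day is after E on either reading, so the overlap is 0 for every visit day.

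**The case against.** The day count is not in dispute; the case against is about consequence.

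- **The vaccine comes after the Day 29 sample**, so it cannot alter the primary titer. PP exclusion is discretionary under 6.5.3, and the PP definition asks for a major deviation affecting the immune response. This stands, and it means exclusion is a possibility only. But SAP 6.3.6 leaves the deviation rules to be settled before database lock, so a foreseeable case, created by following the protocol, is left to later judgment.
- **Day 181 is barely protected.** Another vaccine from Day 30 is allowed with or without the change. This stands; the change should not be justified by Day 181 data.
- **AE capture is limited after an early visit.** The row "Recording of all unsolicited AEs" in Table 1 ends at the Day 29 Visit, and the Day 57 call asks only about SAEs, AESIs, MAAEs and AEs leading to withdrawal. Minor events may be missed, partly because of the −7 day window itself, which this change leaves alone. This stands in part: 8.4.14 keeps collection open, and a medically attended reaction with onset inside the 28 days would still enter the SAP 6.4.1 tables.
- **Exclusion 12 already removes planned vaccinations.** It covers plans at entry. Section 5.3 itself foresees a participant choosing a vaccine later, so those decisions remain.
- **Section 5.3 is a minimum restriction, not permission.** The two rules can coexist on paper, but a participant told to wait for the visit has no reason to know of a longer limit in 6.5.3.
- **Overlaps are visible.** Non-study vaccinations are recorded (Protocol 6.5.2) and summarized (SAP 6.3.4), investigators assess causality, and blinding gives no reason to expect uptake to differ by arm. This limits the harm but does not remove the overlap.

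**Conclusion.** The concern holds. No other provision sets a 28-day floor on deferral, so 5.3 conflicts with the plan's own 28-day periods on either reading of their last day. An overlap is possible after 6 to 8 of the 10 permitted visit days, and lasts at most 6 to 8 days, after a Day 22 visit. The range rests on two assumptions the documents do not settle: whether the period ends on Day 28 or Day 29, and whether the other vaccine can be given on the visit day.

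These figures measure opportunity, not exposure. The documents give no rate of early visits or of non-study vaccination, and the number affected is probably small. The point is a worthwhile correction of modest size, not a threat to the validity of the study.

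**What to change.** Change 5.3 so that other licensed or authorized vaccines are deferred until the later of two dates: completion of the Day 29 Visit, and the end of the 28-day period used in 6.5.3. Name the day. Day 29 onward is enough if the period means injection day + 27; Day 30 onward clears both readings and is the safer choice. Carry the same day into the participant instruction. Section 6.5.3 and the SAP need no change.

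The cost is one protocol sentence and the matching instruction, with no new data or tables. After a Day 22 visit a participant waits at most 30 − 22 = 8 days longer with a Day 30 start, or 29 − 22 = 7 days longer with a Day 29 start; each is one day less if the vaccine could not have been given on the visit day. Visits on Day 30 or 31 add no wait.
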